2. AIM 1: GROUP SELF-TESTING

2.1. OBJECTIVES

2.1.1. Primary Objectives:

- To determine whether group self-testing in waiting areas of outpatient departments (OPD) and sexually transmitted infection (STI) clinics is superior in regard to number tested compared to optimized standard of care (provider-initiated-testing-and-counseling; PITC)
- To determine whether group self-testing in waiting areas of OPD and STI clinics is cost-effective compared to optimized standard of care using PITC

2.1.2. Secondary Objectives:

- To assess the acceptability of self-testing in waiting areas of OPD and STI clinics
- To determine whether group self-testing in waiting areas of OPD and STI clinics is superior in regard to number of HIV+ individuals identified (testing yield)
- To determine whether group self-testing in waiting areas of OPD and STI clinics is superior in regard to linkage rates for those who identify as HIV-positive compared to standard of care and optimized standard of care (PITC)

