Those who choose to participate in self-testing will be asked to keep the used kit in an opaque bag and give the anonymized self-test kit to the study team during the brief exit survey. The study team will NOT look at the test results, but will staple the opaque bag closed, link the unique identification number on the test bag to the exit survey, and drop the self-test kit into a secure lockbox. Those who do not want to directly give the self-test kit to the study team will be allowed to dispose their test kit in a lockbox located in the waiting area or a lockbox located in the provider consultation room.

After completing the OPD or STI consultation, clients aged 15 years and older will be asked to participate in a brief 15 minute, anonymized exit survey about their experience with self-testing why they chose to use the kit or not. We will recruit all eligible OPD and STI clients for the survey – including clients who used self-testing and those who opted-out of self-testing. Survey participation is completely voluntary and can be refused at any point. Those who self-report as testing HIV positive with a self-test kit will complete written consent and will provide identifiable information so the study can prospectively track linkage to care.

HIV testing registers, ART registers, OPD registers, and STI registers will be reviewed to triangulate the (1) number of individuals attending OPD and STI clinics over the study period (denominator), (2) number of OPD and STI clients tested for HIV (numerator), (3) proportion of those tested who are identified as HIV-positive (defined as a positive HIV test from two different types of tests – Determine and Uni-Gold), and (4) proportion of those identified as HIV-positive who linked to ART services. All data will be anonymized from existing registers. Records from OPD and STI clients aged 15 years and older will be included in the study. Over the study period, we will be able to determine the proportion of all STI and OPD patients who receive an HIV test, the proportion of those tested who are HIV-positive, and the proportion of HIV-positive clients who link to ART services. We will also be able to determine differences by age sex, and service type.

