2.4.2. Optimized Standard of Care Arm

2.4.2.1 *Provider Initiated Testing and Counseling (PITC)*

Facilities randomized to the optimized standard of care arm will provide standard PITC as recommended by the Ministry of Health. Facilities will be supported by the study team with initial trainings on the importance of HIV testing, the role of HIV testing as part of outpatient and STI care, and strategies used to discuss HIV testing with patients. The study team will also provide job aids to remind providers about the importance of referring patients for HIV testing and assist in the monitoring and evaluation of PITC implementation. When clients are referred for testing, they will use the standard HIV testing services room located in the same health facility. Testing will be available during all clinic hours and completed by trained HIV Diagnostic Assistants (HDA) who work at the facility (i.e., non-study staff). HIV testing for OPD and STI clients will follow Ministry of Health National Guidelines using HDAs who will provide individual counseling and serial testing with Determine and Uni-Gold HIV test kits. Discordant results will result in re-testing using the MOH guidelines. Those with positive HIV tests will be counseled and referred to ART services following routine care.

2.4.2.2. *Demographic Data Collection*

Clients in the optimized standard of care arm who complete an OPD/STI consultation visit will meet briefly with a study staff member after their visit. The study staff member will collect anonymous demographic data including age, gender, highest level of education, and reason for visit to OPD/STI clinic. It will also capture if clients were offered testing, if they were tested, self-reported test result, and why they chose to test or not.

2.4.2.3 *Additional Data Collection for those who: (1) test HIV positive that same day; (2) have not tested but want to test for HIV that same day, Participants who self-report as having (1) tested HIV positive that same day or (2) not tested but want to test for HIV that same day* will be asked to complete written consent for collection of identifiable information in order to track linkage and retention to ART.

2.4.2.3. *Registry Data for Triangulation and Linkage*

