- Individuals will be asked to give the anonymized self-test kit to the study team during the brief exit survey. The study team will NOT look at the test results, but will staple the opaque bag closed, link the unique identification number on the test bag to the exit survey, and drop the self-test kit into a secure lockbox. Those who do not want to directly give the self-test kit to the study team will be allowed to dispose their test kit in a lockbox located in the waiting area or a lockbox located in the provider consultation room.

Trained research assistants and an HDA will be available in the waiting area to answer any questions.

2. *Test Interpretation and Confirmatory Testing*

Participants who test positive with the self-test method and disclose results to the provider will be referred to an HDA to have confirmation testing conducted with routine Ministry of Health testing guidelines. These individuals will receive standard of care counseling by facility HDAs and be referred for ART initiation if their confirmatory HIV test is positive.

2.4.3.4. *Demographic Data Collection*

Participants in the group self-test arm who complete an OPD/STI consultation visit will meet briefly with a study staff member after their visit. The study staff member will collect anonymous demographic data including age, gender, highest level of education, and reason for visit to

OPD/STI clinic. They will also ask whether or not participants performed the HIV self-test, what motivated them to use/not use the self-test, and self-reported test result (if willing to disclose). For those willing, the study staff member will also collect the self-test kit, staple the opaque bag closed (if used), link the unique identification number on the test bag to the exit survey, and drop the self-test kit into a secure lockbox. The study staff member will NOT look at test results.

2.4.3.4 Additional Data Collection for those who: (1) test HIV positive that same day; (2) have not tested but want to test for HIV that same day

Participants who self-report as having (1) tested HIV positive that same day or (2) not tested but want to test for HIV that same day will be asked to complete written consent for collection of identifiable information in order to track linkage other HIV services.

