2.4.4.1. Registry Data for Triangulation and Linkage

HIV testing, ART, OPD, and STI registers will be reviewed to measure the number of individuals attending the clinics during the period of the study (denominator), the number HIV tested using routine testing strategies (numerator), the proportion of those tested through routine test strategies who are identified as HIV-positive (yield), and the proportion of those identified as HIV positive who link to ART services. All data will be anonymized from existing registers. Records from OPD and STI clients aged 15 years and older will be included in the study. Over the period of the study, we will be able to determine the proportion of all STI and OPD patients who received a routine HIV test (Determine and Uni-Gold HIV test kits), the proportion of those tested who are HIV-positive, and the proportion of HIV positive clients who linked to ART services.

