3.4.4.3 Follow-up of Partner Self-Testing

The number of index partners tested will be determined based on the number of self-test kits returned to village and health facility lockboxes and triangulated with self-reports from a follow-up survey with the index client. Additionally, partners with a positive self-test kit who present to the facility for confirmatory testing and linkage to care, and/or partners who did not use the self-test kit but present to the facility for HIV testing will be accounted for through the returned referral cards. Like self-test kits, referral cards will be identified with a unique code, allowing the partner to be linked to the index client.

For those who are HIV-positive and present to the clinic for care, the ART register will be reviewed four weeks later to determine if the patient starts ART and presents for their four-week follow-up visit. All data from registers will be anonymized for use by the study team. In addition, index clients will provide self-reports about partner linkage to ART during a follow-up survey.

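### The register measure of ART linkage rests on a denominator that self-test users enter only by disclosing or presenting, and the plan does not say which linkage source carries the comparison between arms

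*Combined protocol and SAP*

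**What the plan says.** Section 2.1.2 sets a superiority objective on "linkage rates for those who identify as HIV-positive compared to standard of care and optimized standard of care (PITC"). Section 3.1.2 sets a similar one for partners against optimized standard of care.

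For Aim 1, section 2.4.4.1 takes from the registers "the proportion of those identified as HIV positive who link to ART services". Section 2.3.2 explains what identified means: "defined as a positive HIV test from two different types of tests", namely Determine and Uni-Gold. In the self-testing arm the register test count is "the number HIV tested using routine testing strategies (numerator"), so a reactive self-test alone does not enter.

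The routes to that status differ by arm:
- **Provider-initiated testing arms** (2.4.1, 2.4.2). The HDA does the serial testing. For optimized standard of care, "Those with positive HIV tests will be counseled and referred to ART services following routine care".
- **Self-testing arm** (2.4.3). "Participants who test positive with the self-test method and disclose results to the provider will be referred to an HDA" for confirmation. They will then "be referred for ART initiation if their confirmatory HIV test is positive". A used kit may instead go into a lockbox.
- **Aim 2 self-testing arm** (3.4.4.2, 3.4.4.3). A partner with a positive kit who does not want further care is told to leave it in a lockbox. The ART register is reviewed "For those who are HIV-positive and present to the clinic for care".

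There is a second source. Sections 2.3.2, 2.3.3 and 2.4.3 take written consent and identifiers from clients who self-report a positive result, without requiring confirmation, and follow their linkage. In Aim 2, index clients in every arm are asked at follow-up about partners' results and linkage (sections 4.1, 4.2 and 3.4.4.4).

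The statistical sections (2.5.1 and 3.5.1.1) name testing and positivity as outcomes. Neither gives a denominator, model or test for linkage.

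**The concern.** A linkage proportion compares arms fairly only if people enter the denominator in the same way in each. Here a positive client in the comparator arms is known to staff because staff did the test. A positive self-tester is counted in the registers only after two further voluntary steps, disclosing and going for confirmation. Those who keep the result private leave both numerator and denominator, and keeping it private is an obvious way for self-testing to fail to link people to care. The register proportion would then describe the self-testers already moving towards care, set against nearly all positives found in the other arms.

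At stake is a published claim that self-testing links at least as well as, or better than, provider-initiated testing when linkage among all its positives could be lower. Because the plan names no source for the comparison, the choice could also be made after the data are seen.

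**Working it through.** **Figures in the plan.** No linkage, disclosure or confirmation rate is given, so there is no linkage figure to reproduce. The only Aim 1 power statement (2.5.1, at least 95%) concerns testing coverage, and it does reproduce. The design effect is 1 + (1,000 − 1) × 0.004 = 4.996, and the effective size per arm is 5,000 / 4.996 = 1,001. Power for 5% against 10% is 98.9% (two-sided normal) or 96.0% (t with 8 df), and for 10% against 60% about 100%. This does not bear on linkage.

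**Set-up (all four quantities are assumptions).**
- c: share of positive self-testers who disclose and are confirmed
- l: linkage among the confirmed
- m: linkage among the unconfirmed
- L0: linkage in the provider-initiated testing arm

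The register measure reports l whatever c is. Linkage among all positive self-testers is

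T = c·l + (1 − c)·m.

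The overstatement is l − T = (1 − c)(l − m), which is positive when m < l and zero when m = l. The documents point to m < l, because ART referral in section 2.4.3 depends on a positive confirmatory test, but they give no value.

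**Size of the gap at l = 0.80** (the register measure shows 0.80 in every row):

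| c | T if m = 0 | T if m = 0.2 |
|---|---|---|
| 0.9 | 0.72 | 0.74 |
| 0.8 | 0.64 | 0.68 |
| 0.6 | 0.48 | 0.56 |
| 0.5 | 0.40 | 0.50 |

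**When the ranking reverses.** If l > L0 > m, self-testing looks better on the register measure but is worse overall when

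c < (L0 − m) / (l − m).

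With l = 0.85 and L0 = 0.75:
- m = 0: 0.75 / 0.85 = 0.88
- m = 0.2: 0.55 / 0.65 = 0.85
- m = 0.4: 0.35 / 0.45 = 0.78

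Over L0 of 0.6, 0.7 and 0.8, l of 0.7, 0.8 and 0.9, and m of 0, 0.2 and 0.4, keeping only cases with l > L0, the break-even c runs from 0.40 to 0.89. If l ≤ L0 the register measure does not favour self-testing and there is nothing to reverse. One case without reversal: c = 0.80, l = 0.85, m = 0.40 gives 0.80 × 0.85 + 0.20 × 0.40 = 0.76, above 0.75.

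**Would ART starts per attendee be enough alone?** Take the coverage assumptions in 2.5.1 (60% and 10%), equal positivity p among those tested, and a poor linkage case for self-testing (c = 0.50, l = 0.85, m = 0, so T = 0.425):
- Self-testing: 0.60 × p × 0.425 = 0.255p
- Optimized standard of care: 0.10 × p × 0.75 = 0.075p

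The ratio is 3.4 in favour of self-testing although its linkage is much worse. The measure has a common denominator, but it answers a different question and cannot replace the linkage comparison.

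**The case against.** A reader might infer that the plan computes linkage only among confirmed positives. The documents do not support that. In Aim 1 every arm's exit survey leads to tracking of self-reported positives, and in the self-testing arm this needs no confirmation. The objective's wording, those who identify as HIV-positive, fits that group at least as well as the register group. In Aim 2 the register review is supplemented by index-client reports, collected in all three arms. With no linkage analysis specified, the plan cannot be said to have chosen the biased measure. Every rate in the reversal calculation is assumed.

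All of this stands, and it narrows the point without removing it. The survey group depends on willingness to report a result and to sign consent, and study staff do not look at the kit result at the exit survey. A self-tester who tells neither the provider nor the survey staff is missing from both sources, whereas a comparator client who says nothing at exit still appears as a positive in the testing register. Index-client reports depend on what the index client knows and is willing to say. Having two unequal sources and no rule for choosing between them is itself a defect in a superiority objective.

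**Conclusion.** The point holds in a limited form. The register linkage measure in Aim 1, and the ART-register review of presenting partners in Aim 2, condition on a step after randomization that differs by arm. They tend to favour self-testing provided unconfirmed positives link less often than confirmed ones. That condition is likely from the referral pathway but is not quantified in the documents.

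It would be tempting to conclude that linkage is certainly overstated, or that the comparison will come out the wrong way round. Neither follows. There is no overstatement if unconfirmed positives link equally often. Reversal also requires confirmed self-testers to link better than comparator clients and the confirmed share to be below the break-even value: about 88%, 85% or 78% in the 85% against 75% example. These inputs are not extreme, but none comes from the plan.

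Linkage is secondary in both aims, so the primary testing comparison is untouched. The change should be made because it is cheap and the present wording leaves the choice of denominator open.

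**What to change.** State in sections 2.5.1 and 3.5.1.1:

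1. **Linkage comparison.** Aim 1: all clients self-reporting a positive result in the exit survey. Aim 2: all partners reported positive by index clients at follow-up. Use the same rule in every arm, counting anyone not confirmed, or not found in ART registers or reports, as not linked. Report the share confirmed by arm. Add a sensitivity range for undisclosed positives, varying both the positivity among self-testers who withheld their result and their linkage.
2. **Combined measure alongside.** ART starts per OPD/STI attendee (Aim 1) and partner ART starts per index client (Aim 2), labelled as the joint effect of testing, yield and linkage, not as linkage.
3. **Register-confirmed linkage.** Report it by arm as descriptive only, with no superiority test.

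Cost: the attendee counts, register data and survey-tracked positives are already planned, so this is mainly analysis text. Intervals will be wider because ART starts per attendee are few. Some false-positive self-tests will be counted as not linked, which works against self-testing, so the confirmed share should be shown beside the result. Attribution of ART starts must be checked, as the existing measure already requires. Registers are anonymized, section 2.3.3 limits identifiers to self-reported positives and those wanting a test, and no link from a comparator-arm partner test to an individual index client is described. If attribution fails for undisclosed self-testers, the combined measure keeps some of the disclosure condition and the report should say so.

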2.4.6.2. Focus Group Discussions with Providers

At the end of Aim 1 implementation, focus group discussions will be conducted with providers at participating OPD, STI, and HTC clinics to understand perceptions and acceptability of group self-testing at OPD and STI clinics. All core providers and supporting staff involved with the self-test intervention will be asked to participate (estimated 5 providers and 8 supporting staff at each site). Each site will complete two focus groups; one with providers and one with supporting staff (10 focus groups in total). Only providers over 18 years of age, actively involved in the self-test intervention, and willing and able to consent will participate. Focus groups will last approximately 45 minutes.

2.5. STATISTICAL METHODS

2.5.1. Outcome Measures

Power Calculations and Statistical Analysis for Primary Outcome Measures

We have 15 clusters available for randomization, and therefore, estimated our sample size assuming a fixed number of clusters (k) and an equal number of clusters per arm (k=5). We also assumed an equal number of participants per cluster (n=1,000) for a total sample size of 5,000 participant per arm (15,000 total). Assuming a type I error of 0.05, an intra-cluster correlation of 0.004, we would expect at least 95% power to detect study arm testing coverage of 5% in study arm 1, at least 10% in study arm 2, and 60% in study arm 3.

We will calculate descriptive statistics, including mean/median, variation (standard deviation, kurtosis), range, and frequency distributions for the demographic and clinical characteristics, overall and by study arm. The outcomes of interest include the proportion of participants tested and HIV-positivity among those tested. Differences in the prevalence of each of the outcomes of interest will be examined by study arm as well as by other factors of interest including demographic characteristics (e.g., age, gender), clinical characteristics (e.g., reason for clinic visit), and structural factors (e.g., geographic location). The differences will be evaluated using t-tests, Mann-Whitney U test (or other non-parametric tests), chi-square methods, and Fisher's exact test as appropriate. In order to assess factors associated with HIV testing/positivity, we will use hierarchical linear models in order to account for clustering of effects within each clinic. Separate models will be developed for each outcome of interest and covariates of interest include patient characteristics (e.g., age, gender) and other structural and contextual factors.

Qualitative Analysis for Secondary Outcome Measures

Our secondary outcomes measured will be feasibility and acceptability of group self-testing including privacy concerns, problems with performing or interpreting self-tests, and perceived harms or benefits resulting from self-testing. Qualitative methods (semi-structured in-depth interviews) will be conducted on a subset of individuals (n=40) from the group self-testing arm. Interviews will be translated and transcribed by trained personnel. Interviews will be analyzed in Atlas.ti v.6.2 using thematic analysis. Two investigators will code the first five interviews by themes and compare coding to reach a consensus. A codebook will be developed, and two coders will independently code all transcripts and compare codes to reach a consensus. For each theme, we will describe the range, central tendency, and context in which each theme emerges.

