3. HYPOTHESES

- Aim 1: Group self-testing will (1) increase the number of OPD and STI clients tested for HIV, (2) increase HIV testing yield, and (3) be cost-effective compared to the optimized standard of care
- Aim 2: Self-test kits given to index clients will (1) increase the number of index partners who test for HIV; (2) increase yield of partner testing, and (3) be cost-effective compared to the optimized standard of care for partner notification and testing, and will (4) increase partner disclosure by the index client

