HIV testing, ART, OPD, and STI registers will be reviewed to measure the number of individuals attending the clinics during the period of the study (denominator), the number HIV tested (numerator), the proportion of those tested who are identified as HIV-positive (yield), and the proportion of those identified as HIV positive who link to ART services. All data will be anonymized from existing registers. Records from OPD and STI clients aged 15 years and older will be included in the study. Over the period of the study, we will be able to determine the proportion of all STI and OPD patients who receive an HIV test, the proportion of those tested who are HIV-positive, and the proportion of HIV positive clients who linked to ART services.

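### The Aim 1 yield objective is a number of HIV-positive people identified, but the yield outcome named for comparison by arm is positivity among those tested, with an inconsistent denominator in the self-test arm

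*Combined protocol and SAP*

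**What the plan says.** The secondary objectives of Aim 1 (Schema and Section 2.1.2) ask whether group self-testing is "superior in regard to number of HIV+ individuals identified (testing yield"). The Aim 1 hypothesis says that it will "increase HIV testing yield, and (3) be cost-effective compared to the optimized standard of care", without saying whether yield is a count or a proportion.

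Section 2.5.1 states the analysis: "The outcomes of interest include the proportion of participants tested and HIV-positivity among those tested". Its comparisons by arm, its tests and its hierarchical models are written for those outcomes. The secondary outcomes listed after it are feasibility and acceptability, assessed qualitatively. The planned coverage is 5% in arm 1, "at least 10% in study arm 2, and 60% in study arm 3".

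Elsewhere, yield is a proportion, and its denominator varies:
- Optimized standard of care arm, registry data (Section 2.4.2): "the proportion of those tested who are identified as HIV-positive (yield").
- Self-test arm, registry data (Section 2.4.4.1): "the proportion of those tested through routine test strategies who are identified as HIV-positive (yield").
- Recruitment text, including the self-test arm (Section 2.3.2): "proportion of those tested who are identified as HIV-positive (defined as a positive HIV test from two different types of tests", here without the yield label.

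The number of positives reappears in Sections 2.6 and 2.6.2, where cost per HIV-positive person identified is compared between arms and a ratio of cost difference to effectiveness difference is planned.

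**The concern.** The objective and the outcome named for it are different quantities. The number identified depends on how many people are tested and on how many of those are positive. Positivity keeps only the second factor and conditions on the first, which is what the intervention acts on. If self-testing reaches many more people, including some at lower risk, it can find more positives while positivity falls.

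The self-test arm adds a second difficulty. Section 2.4.3 says: "Participants who test positive with the self-test method and disclose results to the provider will be referred to an HDA", where routine confirmatory testing follows. Routine tests in that arm therefore include people selected because they had already screened positive. Positive self-tests that are not disclosed do not reach this step; they would count among those tested but not among the confirmed. One denominator pulls positivity up and the other pulls it down, and no rule says how survey, kit and register sources are combined.

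At stake is whether the trial can support its claim that self-testing identifies more HIV-positive people than optimized standard of care.

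**Working it through.** **The plan's own figure.** Section 2.5.1 gives 5 clusters of 1,000 per arm, ICC 0.004, type I error 0.05 (taken as two-sided) and at least 95% power for coverage of 5%, 10% and 60%. The design effect is 1 + 999 × 0.004 = 4.996, so the effective size per arm is 5,000/4.996 = 1,000.8. For 5% against 10%, power is 98.9% (normal) or 96.0% (t, 8 df); for 10% against 60% it is about 100%. The stated power reproduces, but it concerns coverage only. No power is given for yield.

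**Step 1: when number and positivity disagree, with all tests in the denominator.** Let c be confirmed positivity among all those tested, self-tests included. Arm 3 finds more positives if 0.60 × c3 > cov2 × c2, that is, if c3/c2 > cov2/0.60. It shows lower positivity if c3/c2 < 1. The two disagree in between:

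| Arm 2 coverage | Ratio c3/c2 at which arm 3 finds more but shows lower positivity |
|---|---|
| 10% (stated minimum) | 1/6 to 1 |
| 20% (assumed) | 1/3 to 1 |
| 30% (assumed) | 1/2 to 1 |

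The first row uses the plan's coverage figures and no assumed prevalence.

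**Step 2: an illustration under different denominators.** The documents give no positivity for OPD/STI clients, so these inputs are assumptions:
- 6% positivity among routine tests in both arms;
- 4% or 6% positivity among self-tests;
- 50% or 80% of positive self-tests disclosed and confirmed;
- d = 100, 250 or 500 of 5,000 attendees in arm 3 tested directly by routine tests, inside the 60% total of 3,000;
- every confirmatory test positive.

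This makes 12 combinations. Confirmed positives in arm 3 are (3,000 − d) × self-test positivity × share confirmed + 0.06 × d. They run from 2,900 × 0.02 + 6 = 64 to 2,500 × 0.048 + 30 = 150. Arm 2 has 500 × 0.06 = 30 at 10% coverage, 60 at 20% and 90 at 30%.

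| Definition of positivity in arm 3 | Lowest | Highest | Arm 2 |
|---|---|---|---|
| Confirmed positives / all 3,000 tests | 64/3,000 = 2.1% | 150/3,000 = 5.0% | 6% |
| Confirmed positives / routine tests only (direct + confirmatory) | 80/550 = 14.5% | 145.2/239.2 = 60.7% | 6% |
| Self-reported self-test positives + direct positives / all tests | (2,900 × 0.04 + 6)/3,000 = 4.1% | 6.0% | 6% |

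- All tests: number and positivity point opposite ways in 12 of 12 combinations with arm 2 at 10% or 20%, and in 9 of 12 at 30%.
- Routine tests only: none at 10% or 20%. At 30%, 3 of 12 disagree the other way: arm 3 finds fewer (64, 70 or 80 against 90) but shows higher positivity.
- Self-reported results: the six combinations with 6% self-test positivity show no difference from arm 2.

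**Step 3: precision for the number.** Use positives per attendee, 1,000 per cluster, ICC 0.004 assumed to carry over, and a two-sided 0.05 t-test on 8 df. Arm 2 at 10% coverage gives 30/5,000 = 0.60%. Power is 29% against 1.28% (64/5,000), 67% against 1.98% (98.8/5,000) and 94% against 3.00% (150/5,000). The 95% interval half-width for the first contrast is about 1.0 percentage point. Its power is 59% at ICC 0.001 and 16% at 0.01. With arm 2 at 20% coverage (1.20%), the three powers are 5%, 23% and 69%.

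**The case against.** The strongest reply is that the information is not lost. Coverage and positivity are both compared by arm, registers supply attendees, tests and positives, and the number is their product. A reader who sees 60% against 10% coverage is unlikely to conclude that fewer positives were found. The outcome list is introduced by a word that leaves it open, and yield often means positivity in this field. This stands in part: the number can be derived. But the plan does not say that it will be, separate comparisons of two factors do not give an interval for their product, and the product requires a single denominator.

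A reader might infer that the plan contains no between-arm estimate of the number at all. The documents do not support that. The incremental ratio in Section 2.6.2 most sensibly implies a between-arm difference in positives identified, although the measure is loosely worded there. What is missing is an effect estimate reported in its own right, an interval and a clustering rule.

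A reader might also infer that positivity will answer the objective in the wrong direction. That does not follow either. It depends on a denominator the plan leaves unsettled, and the illustrative grid shows possibility, not likelihood.

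**Conclusion.** The mismatch holds and should be corrected. The objective concerns a number; the outcome named for comparison is a proportion conditional on testing, with two competing denominators in the self-test arm. Over all tests, number and positivity disagree whenever the positivity ratio of arm 3 to arm 2 is between 1/6 and 1 (coverage 10% and 60%). Over routine tests only, positivity in arm 3 is inflated, to 14.5–60.7% against 6% in the illustration. Positivity therefore cannot be relied on to answer the stated objective in either direction.

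The text mismatch and the 1/6 to 1 band rest on the documents alone. The other magnitudes rest on assumed positivity, confirmation and direct-testing rates, and on arm 2 coverage above its stated minimum where 20% or 30% is used. Only a secondary objective is affected; the primary outcome, testing coverage, and its stated power are not.

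**What to change.** For the yield objective, name as the outcome confirmed HIV-positive people (Determine and Uni-Gold) per OPD/STI attendee aged 15 or older, from the same register source in all three arms. State optimized standard of care as the main comparator, as the hypothesis and Section 2.6 already do. Estimate the difference at cluster level (5 facilities per arm, 8 df for a two-arm comparison) with a confidence interval.

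Report positivity among those tested as descriptive, with one stated denominator that includes self-tests in arm 3. Make Sections 2.3.2, 2.4.2, 2.4.4.1 and 2.5.1 agree, and remove the yield label from the routine-only proportion. If positivity is what the sponsor means, reword the objective instead.

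The cost is mainly wording, because attendees and confirmed positives are already to be taken from registers in every arm. There are two downsides. Power for modest differences is probably low and depends strongly on the ICC and on arm 2 coverage, so the aim should be an estimate with an interval and not a powered test. Registers also miss positive self-testers who do not disclose, or who confirm later or elsewhere, which undercounts arm 3. Self-reported positives from the exit survey should be shown alongside as supportive.
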